9.1.3. Hammersmith Functional Motor Scale Expanded

The HFMSE is a reliable and validated tool used to assess motor function in children with SMA. The scale was originally developed with 20 scored activities and was devised for use in children with Type II and Type III SMA with limited ambulation to give objective information on motor ability and clinical progression [Main 2003]. The expanded scale includes an additional module of 13 items developed to allow for the evaluation of ambulatory patients with SMA [O'Hagen 2007]. The HFMSE has been shown to be highly correlated with other clinical assessments and has shown good test-retest reliability.

Whenever possible, for each participant, HFSME assessments across all study visits should be conducted consistently by the same clinical evaluator.

9.1.4. Revised Upper Limb Module

[figure not shown]
Participants with later-onset SMA will be evaluated using the RULM [Mazzone 2016]. The RULM will continue to be performed should participants subsequently become ambulatory.

[figure not shown]
The RULM is an outcome measure developed to assess upper limb functional abilities in patients with SMA, including young children, and patients with severe contractures in the lower limbs in whom the possibility of detecting functional changes, such as rolling or long sitting, is limited. This test consists of upper limb performance items that are reflective of activities of daily living (i.e., raise a can to the mouth as if drinking, take a coin and place it in a box, and remove the lid

of a container). The RULM is quickly administered and has been evaluated in patients with SMA 2 to 52 years of age [Mazzone 2016].

The purpose of an upper limb scale for use in SMA is to assess the change that occurs in the motor performance of the upper limb over time. Motor performance in SMA is defined as a demonstrated ability to perform a skill under certain test conditions. This performance changes with disease progression and/or intervention (including surgery) and is based on the observed response on the day of the assessment. Motor performance will be impacted by muscle strength, contractures, and maturational development (e.g., puberty), and the RULM aims to incorporate the performance of the shoulder, elbow, wrist, and hand.

Whenever possible, for each participant, RULM assessments across all study visits should be conducted consistently by the same clinical evaluator.

9.1.8. Clinical Global Impression of Change

The CGIC rating scale was developed as a brief standalone assessment of the clinician's view of the patient's global functioning after initiating a study medication [Guy 1976]. The CGIC provides an overall clinician-determined summary measure that takes into account all available information, including knowledge of the patient's history, psychosocial circumstances, symptoms, behavior, and the impact of the symptoms on the patient's ability to function. The CGIC is administered by an experienced clinician who is familiar with the disease under study and the likely progression of treatment. The clinician makes a judgment about the total picture of the patient at each visit: the severity of the illness, the patient's level of distress and other aspects of impairment, and the impact of the illness on functioning. The CGIC is rated without regard to the clinician's belief that any clinical changes are or are not due to medication and without consideration of the etiology of the symptoms.

The CGIC is a 7-point scale that requires the clinician to assess how much the patient's illness has changed relative to a baseline state at the beginning of the intervention and is rated as follows: 1, very much improved; 2, much improved; 3, minimally improved; 4, no change; 5, minimally worse; 6, much worse; or 7, very much worse.

CGIC should be assessed consistently by the same rater for each study participant. A separate CGIC assessment will be performed by the Investigator (Principal Investigator or Subinvestigator) and caregiver. Adult participants who do not require a caregiver during the study visits will only have the CGIC assessment assessed by the Investigator.

9.1.9. Parent Assessment of Swallowing Ability

Dysphagia will be assessed in Parts A and B at the timepoints specified in the Schedule of Activities (Table 1 and Table 2) using the PASA questionnaire. Caregivers will be asked a series of questions regarding the mealtime behavior of the participant.

The PASA questionnaire was developed by a Biogen team in order to assess the signs and symptoms of dysphagia. This questionnaire consists of 33 items across 4 domains that cover

general feeding, drinking liquids, eating solid foods, and assessment of swallowing concerns. The first 3 of these domains are generally assessed with 5 levels of response (Never, Rarely, Sometimes, Often, and Always), although 2 items are assessed with a simple "Yes"/"No" answer. In the final domain, the assessment of swallowing concerns has 4 levels of response: Strongly Agree, Agree, Disagree, and Strongly Disagree. In answering each item, the caregiver is directed to consider the previous 7 days.

9.1.10. Quality-of-Life Questionnaires

QoL questionnaires include the PedsQL, ACEND, QoL questionnaires will be collected on the days specified in Table 1, Table 2, Table 3, and Table 4.

9.1.10.1. Pediatric Quality of Life Inventory (Generic Core Scales and Neuromuscular Module)

Participants with later-onset SMA will be evaluated using the age-appropriate modules of the PedsQL Measurement 4.0 Generic Core Scales and 3.0 Neuromuscular Module [Varni 1999], which include age 2 to 4 years, 5 to 7 years, 8 to 12 years, 13 to 18 years, 18 to 25 years, and ≥ 26 years. This assessment has been validated by the American Spinal Muscular Atrophy Randomized Trials Group [Iannaccone 2009].

The PedsQL Measurement Model is a modular approach to measuring HRQOL in children, adolescents, and adults. The PedsQL consists of brief, practical, generic core scales, as well as condition-specific modules for use in designated clinical populations. The PedsQL 4.0 Generic Core Scales include an assessment of physical functioning, emotional functioning, social functioning, and school functioning and will be assessed for participants 2 to \geq 26 years of age. The PedsQL 3.0 Neuromuscular Module was designed to measure HRQOL dimensions specific to patients with neuromuscular disorders, including SMA, and will be assessed in participants 2 to 25 years of age. Patient self-report will be measured in participants starting at 5 years of age, while parent proxy-report of HRQOL will be measured for participants starting at 2 years of age.

In Parts A and B, all participants with later-onset SMA will be evaluated using the PedsQL. In Part C Cohort 1, the PedsQL (in addition to ACEND) will be evaluated in participants who are ≥ 2 years of age at Screening. The PedsQL will not be evaluated for participants in Part C Cohort 2.

If a participant is assessed on PedsQL at baseline, then the age range of the scale used at Screening for that participant will continue to be used up to Day 302, regardless of changes in the participant's age.

9.1.10.2. Assessment of Caregiver Experience With Neuromuscular Disease

Parents/caregivers of participants will complete the ACEND questionnaire. The ACEND questionnaire will not be collected for adult participants who do not require a caregiver. This assessment instrument has been designed to quantify the caregiver impact experienced by parents/caregivers of children affected with severe neuromuscular diseases, including children

with SMA [Matsumoto 2011]. ACEND includes domains assessing physical impact (including feeding/grooming/dressing, sitting/play, transfers, and mobility) and general caregiver impact (including time, emotion, and finance).

9.1.14. Ventilator Use

9.1.14.1. All Participants

The participant's ventilator use will be collected at every study visit. If ventilation is used daily, the average number of hours per day for the past 7 days will be recorded (except for participants with infantile-onset SMA enrolled in Part B; see Section 9.1.14.2).

9.1.14.2. Participants With Infantile-Onset SMA in Part B

The participant's ventilator use (number of hours/day) will be recorded daily by the caregiver using a daily ventilator use diary for the duration of the study, regardless of whether or not a ventilator is being utilized. This information will be obtained by the site during study visits and telephone contacts and entered into the CRF.

9.1.15. Standard of Care

All participants are expected to follow standard of care as referenced in Section 6.2 throughout the entire duration of the study. Investigators will document standard of care information for Part B participants at Screening and Day 302.

9.3. Pharmacodynamic Assessments

The PD properties of nusinersen will be assessed (where data are available) by evaluating the plasma and CSF levels of NF-L to explore its role as a potential biomarker of treatment response in SMA.

9.5. Pharmacogenetic and Genetic Assessments

All participants will undergo genetic testing through a central laboratory to confirm *SMN1* status (copy number, deletion, and mutation where necessary to confirm 5q SMA) and *SMN2* copy number. For the purpose of determining study eligibility, historical genetic testing results may be acceptable with appropriate documentation or analysis may be performed at a local laboratory if needed, but confirmatory testing through a central laboratory will also be performed. Deoxyribonucleic acid is to be collected from all participants to assess sequence variations at the *SMN1* and *SMN2* loci that might affect *SMN1* and *SMN2* activity or the binding of nusinersen.

9.6. Future Scientific Research Assessments

The samples collected may be utilized to identify or verify putative, prognostic, and predictive markers associated with disease and markers of therapeutic response to treatment, and/or to develop diagnostic and analytical tests. Background and dynamic clinical disease characteristics and associated biomarker data may be utilized to predict subsequent disease worsening (severity), identify high-risk patient subgroups, and identify predictors of response to treatment.

10. SAFETY ASSESSMENTS

See Section 1.3 for the timing of all safety assessments.

Tests and evaluations affecting primary endpoints and/or analyses may need to be repeated if the original results are lost or damaged. In these cases, participants will be asked to return to the study site to have the evaluations repeated.

10.1. Clinical Safety Assessments

The following clinical assessments will be performed to evaluate the safety profile of nusinersen:

- AE and SAE recording
- Medical (including SMA) history.
- Vital sign measurements: temperature, pulse rate, systolic and diastolic blood pressure, respiratory rate, and pulse oximetry
- Growth parameters: body length/height (for all participants; body length will be
 measured for participants who are not able to stand independently), head, chest, and
 arm circumference (for participants with infantile-onset SMA), and ulnar length (for
 participants with later-onset SMA) will be measured. Additional parameters of
 weight-for-age, weight-for-length, and head-to-chest circumference ratio will be
 calculated.
- Neurological examinations: HINE Sections 1 and 3 will be administered to participants in Part B with infantile-onset SMA, and participants in Part C < 2 years of age at the time of informed consent. A neurological examination will be performed in participants in Parts A and B with later-onset SMA and participants in Part C ≥ 2 years of age at the time of informed consent.
- Physical examinations (videotaping of physical examinations is optional)
- ECGs
- LP opening pressure: Details available in the DHA. LP opening pressure will be evaluated for all participants in Parts A and C, but only for participants with later-onset SMA in Part B.
- Concomitant therapy and procedure recording

10.2. Laboratory Safety Assessments

Samples will be analyzed using Good Laboratory Practice-validated assays.

The following laboratory assessments will be performed to evaluate the safety profile of nusinersen:

- Hematology: complete blood cell count, with differential and platelet count, and absolute neutrophil count
- Coagulation parameters (by local laboratory): aPTT, PT, and INR
- Blood chemistry: total protein, albumin, creatinine, blood urea nitrogen, bilirubin (total and direct), alkaline phosphatase, alanine aminotransferase, aspartate aminotransferase, gamma-glutamyl transferase, glucose, calcium, phosphorus, bicarbonate, chloride, sodium, potassium, cystatin C, creatine phosphokinase, and creatine kinase
- Urinalysis: urine total protein (by local laboratory except if local analysis is not possible without a 24-hour urine collection, in which case samples will be analyzed by a central laboratory); specific gravity, pH, protein, glucose, ketones, bilirubin, blood, red blood cells, white blood cells, epithelial cells, bacteria, casts, and crystals
- CSF local laboratory sample: cell count, total protein, and glucose

The laboratory analytes to be measured are shown in Appendix B.

When the safety laboratory sample analysis is at risk due to logistical difficulties or issues with access to the central laboratory (e.g., due to COVID-19–related disruptions or humanitarian emergencies), these samples may be analyzed by the local laboratory. Any use of a local laboratory under these circumstances must be approved by the Sponsor prior to being implemented.

10.3. Telephone Assessments

For all study parts, from 2 to 14 days after each maintenance dose, participants will be contacted via a telephone call to capture any clinical changes, such as new AEs, ventilator use/status updates, and changes in concomitant therapies. Telephone calls will also be made in Part A 2 weeks (± 3 days) after the Day 29 dose, in Part B 2 weeks (± 3 days) after the Day 29 dose for the first 20 participants, and in Part C 2 weeks (± 3 days) after the Day 1 bolus dose.

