- ⁵ Eligibility based on scoliosis severity at Screening will be determined by local analysis of the X-ray results. Results of the central X-ray read will be documented and used for subsequent data analyses. For sites with local regulation on use of X-ray (e.g., Germany), the Investigator may assess scoliosis based on physical examination without imaging.
- ⁶ LP opening pressure will only be evaluated for participants with later-onset SMA. Only measure LP opening pressure and assess CSF local laboratory sample on Days 1, 15, and 279 to avoid potential unblinding.
- ⁷ Spinal ultrasound, fluoroscopy, or similar techniques may be used for the LP procedure, if deemed necessary, but are not required. Local anesthesia and/or sedation may be used for the LP procedure in participants with infantile-onset SMA, and anesthesia (local or general) and/or sedation may be used for the LP procedure in participants with later-onset SMA, at the discretion of the Investigator and/or study center. If anesthesia and/or sedation is used for the LP procedure for an individual participant, in order to maintain the blind, that participant will receive equivalent anesthesia and/or sedation (according to institutional procedures) for all of the sham procedures and LP injections. For participants with infantile-onset SMA, LP injections/sham procedures may not occur within 72 hours after an immunization.
- ⁸ Participants will remain at the clinic for at least 24 hours after study treatment administration on Days 1 and 15; inpatient stays at other visits may occur based on the Investigator's discretion. If the primary reason for the inpatient stay is due to an AE or SAE, reporting requirements per Section 11.3 must be followed.
- ⁹ Vital signs will include temperature, pulse rate, systolic and diastolic blood pressure, respiratory rate, and pulse oximetry.
- ¹⁰On Days 1 and 15, postdose vital signs will be collected at 1, 2, 4, 6, and 8 hours (± 15 minutes) postdose and at 24 hours (± 2 hours) postdose. On Days 29, 64, 135, 183, and 279, postdose vital signs will be collected at 1 hour (± 30 minutes) and 6 hours (± 1 hour) postdose.

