After 6 participants have completed the loading period (i.e., when the last participant has available safety data through the Day 64 visit), an IDMC will review the available safety data to recommend whether Part B can be initiated. If deemed necessary by the Sponsor, additional participants may be enrolled in Part A to ensure sufficient data are available for the IDMC review prior to enrollment of participants in Part B. Details regarding the IDMC review of data may be found in the IDMC charter. Meanwhile, participants in Part A will proceed to maintenance dosing without interruption. Note that the IDMC can recommend to stop the study based on the safety findings.

Part B will consist of a pivotal, double-blind, active-controlled treatment period with either 2 or 4 loading doses of nusinersen (for the 50/28-mg Group and Control Group, respectively) administered intrathecally followed by maintenance doses approximately every 4 months

thereafter. Approximately 99 participants with infantile- or later-onset SMA will be randomized in a 1:2 ratio to receive either the currently approved dosing regimen of 4 loading doses of 12 mg of nusinersen administered intrathecally (Days 1, 15, 29, and 64) followed by 2 maintenance doses of 12 mg on Days 183 and 279 (Control Group) or 2 loading doses of 50 mg of nusinersen administered intrathecally (Days 1 and 15) followed by 2 maintenance doses of 28 mg on Days 135 and 279 (50/28-mg Group). In order to maintain blinding, 1 sham procedure will be administered in the Control Group on Day 135 and 3 sham procedures will be administered in the 50/28-mg Group on Days 29, 64, and 183 to ensure the same dosing visit schedule as the Control Group. Participants will remain at the clinic for at least 24 hours after study treatment administration on Days 1 and 15; inpatient stays at other visits may occur based on the Investigator's discretion. If the primary reason for the inpatient stay is due to an AE or SAE, reporting requirements per Section 11.3 must be followed.

Randomization in Part B will be performed using IRT. For Part B, the randomization will be stratified as follows:

- For participants with infantile-onset SMA by disease duration: ≤ 12 weeks and > 12 weeks (time from age at symptom onset to age at informed consent)
- For participants with later-onset SMA by age at informed consent: < 6 years and ≥ 6 years

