7. STUDY TREATMENT

7.1. Regimen

Participants will receive treatment as follows:

• Part A: Six participants with later-onset SMA will receive 3 loading doses of 28 mg of nusinersen administered intrathecally on Days 1, 15, and 29. A sentinel dosing approach will be used, in which the first participant will be enrolled and dosed with 28 mg of nusinersen. Following the availability of 72 hours of safety data after the first loading dose in the first participant, data for this participant will be reviewed by the Investigator and the Sponsor before the next 5 participants are enrolled. Only 1 participant can receive their first dose of study treatment on a given day. Maintenance doses of 28 mg of nusinersen will be administered on Days 149 and 269.

Part B:

- Control Group: A total of 33 participants (25 with infantile-onset SMA and 8 with later-onset SMA) will receive 4 loading doses of 12 mg of nusinersen administered intrathecally (Days 1, 15, 29, and 64), followed by maintenance doses of 12 mg on Days 183 and 279 (and a sham procedure on Day 135). See Table 6 for the blinded dosing schedule.
- 50/28-mg Group: A total of 66 participants (50 with infantile-onset SMA and 16 with later-onset SMA) will receive 2 loading doses of 50 mg of nusinersen administered intrathecally (Days 1 and 15) and 2 sham procedures on Days 29 and 64, followed by maintenance doses of 28 mg on Days 135 and 279 (and a sham procedure on Day 183). See Table 6 for the blinded dosing schedule.

Table 6: Part B Blinded Dosing Schedule

Arm	Dose 1	Dose 2	Dose 3	Dose 4	Dose 5	Dose 6	Dose 7
50/28-mg Group	D1 (50 mg)	D15 (50 mg)	D29 (sham)	D64 (sham)	D135 (28 mg)	D183 (sham)	D279 (28 mg) ¹
Control Group (12/12 mg)	D1 (12 mg)	D15 (12 mg)	D29 (12 mg)	D64 (12 mg)	D135 (sham)	D183 (12 mg)	D279 (12 mg) ²

 $[\]overline{D} = dav$

• Part C: Up to approximately 40 participants (i.e., up to approximately 20 participants each in Cohorts 1 and 2) who have already been receiving treatment with nusinersen for at least 1 year prior to entry in this study will receive a single bolus dose of 50 mg of nusinersen administered intrathecally on Day 1 of this study (which should be

¹ Delayed by 24 days from targeted dosing day of D255

² Moved up 24 days from the targeted dosing day of D303

administered 4 months \pm 14 days after their most recent maintenance dose of 12 mg), followed by 2 maintenance doses of 28 mg of nusinersen on Days 121 and 241.

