12.8. Methods of Analysis for Safety Endpoints

The analysis of safety will be performed separately for the Safety Set for Part A, Part B infantile-onset, Part B later-onset, and Part C. In addition, the Part B participants will be presented by treatment group. The duration of treatment and the amount of study treatment will be summarized.

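### Part B schedules a contact within about two weeks of every active 50/28-mg dose, but not of the Control Group's Day 64 dose, nor of its Day 29 dose after the first 20 participants

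*Protocol*

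**What the plan says.** **Active doses.** Section 7.1 states that Control Group participants "will receive 4 loading doses of 12 mg of nusinersen administered intrathecally (Days 1, 15, 29, and 64"), then 12 mg on Days 183 and 279. Section 5.1 gives the other arm two 50-mg loading doses, "Days 1 and 15) followed by 2 maintenance doses of 28 mg on Days 135 and 279 (50/28-mg Group"). Sham procedures are given "in the 50/28-mg Group on Days 29, 64, and 183 to ensure the same dosing visit schedule as the Control Group".

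**Scheduled contacts.** Both arms attend on Days 1, 15, 29, 64, 135, 183, 279 and 302. Section 10.3 adds: "For all study parts, from 2 to 14 days after each maintenance dose, participants will be contacted via a telephone call". The only other Part B call is made "in Part B 2 weeks (± 3 days) after the Day 29 dose for the first 20 participants"; Table 2 footnote 18 repeats it. Nothing is scheduled between Day 64 and Day 135.

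**Observation on the day.** Table 2 footnote 8 says: "Participants will remain at the clinic for at least 24 hours after study treatment administration on Days 1 and 15". Stays at other visits are at the Investigator's discretion. On Days 29 and 64 both arms have vital signs at 1 and 6 hours, a neurological examination at 1 and 3 hours, and an ECG at 5 hours (Table 2 footnotes 10, 14 and 15).

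**Recording and reporting.** Section 11.3.1 has AEs recorded from consent to the last contact and assessed at each visit. For the safety analysis, Section 12.8 says that "the Part B participants will be presented by treatment group".

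**The concern.** A calendar that is the same in both arms is not the same when measured from active injections. On Days 29 and 64 the Control Group receives drug by lumbar puncture (LP), while the 50/28-mg Group receives a skin prick without an injection (Section 7.4). The two long intervals without a scheduled contact therefore follow active doses in the comparator only.

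The events at issue are delayed, non-serious drug or LP reactions: those that begin after the 6-hour check and resolve before the next contact. Continuous recording means that such events should be captured. It does not mean that anyone asks about them while they are fresh.

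AE incidence is a Part B secondary endpoint and is shown by treatment group. If minor post-dose events were under-recorded on 12 mg, the higher dose would look relatively worse than it is.

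**Working it through.** **Check of the plan's own figures (Section 5.2).** Maintenance period: 279 − 64 = 215 days. Shortest follow-up: 302 − 279 = 23 days. Total: 21 + 64 + 215 + 23 = 323 days, and with 120 days of follow-up 21 + 64 + 215 + 120 = 420 days. All agree with the protocol. It states no interval from dose to contact, so these are derived here.

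**Inputs.** Dose days are from Section 7.1 and Table 6. Visit windows are from Table 2: ±1 day for Days 15 and 29, and ±7 days for Days 64, 135, 183 and 279. Calls are from Section 10.3.

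**Interval from each active dose to the next scheduled contact (days)**

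| Active dose | 50/28-mg Group | Control Group |
|---|---|---|
| Day 1 | 15 − 1 = 14 (visit) | 14 (visit) |
| Day 15 | 29 − 15 = 14 (visit; 12 to 16) | 14 (visit; 12 to 16) |
| Day 29 | sham | 64 − 29 = 35 (visit); first 20 participants: call at 14 ± 3 |
| Day 64 | sham | 135 − 64 = 71 (visit) |
| Day 135 | call at 2 to 14 | sham |
| Day 183 | sham | call at 2 to 14 |
| Day 279 | call at 2 to 14 | call at 2 to 14 |

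**Windows on the two long intervals.** Day 29 to Day 64: 35 ± (1 + 7) = 27 to 43 days. Day 64 to Day 135: 71 ± (7 + 7) = 57 to 85 days.

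**Count.** None of the 4 active doses in the 50/28-mg Group lacks a scheduled contact within about two weeks. In the Control Group it is 1 of 6 for the first 20 participants and 2 of 6 for later ones.

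**Who is affected.** The Day 64 interval applies to all 33 planned control participants. If the first 20 Part B participants split 1:2 (an assumption), 20/3 ≈ 7 controls receive the Day 29 call. The 35-day interval then applies to 33 − 20/3 ≈ 26, or 80%.

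**Comparison with the other parts.** Part A calls every participant 2 weeks (± 3 days) after Day 29, Part C does so after the bolus, and maintenance doses in all parts get a call. The two control doses are thus the only active injections in the study without a scheduled contact within about 2.5 weeks (14 + 3 = 17 days).

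**Reading used.** Maintenance doses are taken as the Day 135, 183 and 279 visits in both arms, as Table 2 groups them. Read arm by arm, the wording would move some calls but would still leave none after Day 64.

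**The case against.** The strongest reply is that collection is symmetric. Visits, calls, windows and post-dose checks fall on the same days in both arms under blinding, and AEs are recorded continuously. The 50/28-mg Group has the same 35- and 71-day intervals. In them it can have late effects of two 50-mg doses, reactions to the needle prick or equivalent sedation, and background illness, all recalled over the same time. This stands. A reader might infer that AEs as a whole are collected unequally between arms, and the protocol does not support that. The asymmetry is confined to reactions to the two control injections.

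Three further inferences also go too far.

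- **No contact of any kind until Day 135.** Only scheduled contact is absent. Families hold site telephone numbers for serious events and emergencies (Section 11) and are told to contact the Investigator before any new medication (Section 7.6.1).
- **The higher dose gets fuller 24-hour observation.** Counting only loading doses suggests this. Over all active doses, the required stay covers 2 of 4 in the 50/28-mg Group and 2 of 6 in the Control Group.
- **A percentage of control events is lost.** That needs a capture probability and an AE rate per dose. The protocol gives neither.

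It is also fair to say that the safety comparison is descriptive: Table 8 tests no safety endpoint, and any bias would run against the higher dose rather than hide harm. Section 12.8.1 does plan AE tables by administration status in 90-day intervals. If these are counted from the first dose, the first interval contains all four control loading doses and does not separate the periods that matter.

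**Conclusion.** A minor point that holds in a narrow form. Each active 50/28-mg dose is followed by a scheduled contact within about 14 days. The Control Group's Day 64 dose waits 71 days (57 to 85), and its Day 29 dose 35 days (27 to 43) in everyone after the first 20 Part B participants. Delayed, non-serious reactions to these two doses depend on longer recall, which could lower their recorded frequency on 12 mg.

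The intervals are firm, since they follow from the protocol's visit days. The direction of any bias rests on the assumption that longer recall loses some minor events. Its size cannot be stated from the protocol, and no apparent AE excess on the higher dose can be attributed to it in advance. Serious events, same-day events and background events are not affected differently between arms by this feature.

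**What to change.** In Section 10.3 and Table 2 footnote 18, extend the existing 2-to-14-day safety call to the Day 29 and Day 64 visits for all Part B participants, in place of the Day 29 call for the first 20 only. Both arms are called, so the blind is kept.

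The Version 7 amendment summary, dated June 2024, refers to enrolment in the past tense, so few or no participants may still be ahead of these visits. For those already past them, add to Section 12.8.1 a supplementary by-arm AE table limited to onset in Days 1 to 28 and from Day 279 to the Day 302 visit, shown beside the whole-study incidence. In those windows both arms have active injections on the same days and identical contacts, and the data are already collected.

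The cost is one or two short calls per participant and one extra table. No visit or procedure is added. The calls may raise the AE rate recorded in the Control Group.
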